2.3.2 Values below or above a threshold

Safety values expressed as below the detection limit will be imputed by the value of the detection limit itself. Listings will always show the non-imputed values.

2.3.3 Rounding of variables

Variables will be rounded to the appropriate number of decimals at display level:

- Time since diagnosis will be rounded to 1 decimal.
- Estimated glomerular filtration will be rounded to 2 decimals
- Ratios will be rounded to the number of decimals of the parameter with the least number of decimals.
- Safety laboratory results will be rounded to a maximum of 3 decimal.

2.3.4 Outliers

There will be no outlier detection. All measured values will be included in the analyses.

2.4 PRESENTATION OF RESULTS

2.4.1 Calculation of descriptive statistics and percentages

In tables by analysis visit, only analysis visits with at least 10 subjects (overall) will be shown.

For continuous variables, full descriptive statistics will only be presented if there are at least 2 non-missing observations. Alternatively, only the number of non-missing data points and mean are shown.

	
Statistical Analysis Plan
	

ARGX-113-1705
	
Final Analysis
	
Final 1.0 of 20SEP2022

Descriptive statistics will include the number of non-missing data points, the arithmetic mean, the standard deviation (SD), the median, minimum, Q1, Q3 and maximum.

Mean, median, Q1 and Q3 will be presented with one more decimal place than the individual values. SD will be presented with two more decimal places than the individual values. Minimum and maximum will be presented with the same number of decimal places as the individual values.

For event-type safety data, the number and percentage of patients with an event will be shown. The denominator will be all patients in the analysis set per treatment and cycle. All cycles will be shown, even if no events are present.

For frequency tabulations and cross-tabulations, the denominator will be all patients in the analysis set per treatment. For tables where results are shown by analysis visit, the denominator will be all patients in the analysis set per treatment and per analysis visit. Missing values will never be included in the denominator count when computing percentages. For cross-tabulations of post-baseline results versus baseline results, a ‘missing’ category will be shown for baseline results if applicable.

2.4.2 Presentation of treatments

The following treatment labels will be used in the tables and listings:

- efgartigimod
- placebo-efgartigimod
- Total efgartigimod

Total efgartigimod will be shown last.

2.4.3 Ordering in tables, figures and listings

For presentations by analysis visits, this analysis will only tabulate data collected from the first OLE cycle on. In case a patient starts with ITP0 visits, these will not be considered in the tables. Part B data will not be tabulated separately but will be allocated to cycles like part A data.

All tables will be presented per treatment and cycle, unless specified otherwise. If present, worst-case will be shown last. Cycles will be indicated as a subtitle or within the table like “Cycle n”.

Listings for general characteristics, results will be ordered by treatment and patient, unless specified otherwise.

All other listings will be ordered by treatment, patient, period, analysis visit and time point, unless specified otherwise.

In tables showing several parameters, each parameter will begin on a new page and parameters will be sorted alphabetically, within the parameter category if applicable.

Efgartigimod-efgartigimod group will always be shown first and then Placebo-efgartigimod.

	Statistical Analysis Plan	
ARGX-113-1705	Final Analysis	Final 1.0 of 20SEP2022

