FDA	Food and Drug Administration
FSH	follicle-stimulating hormone
GCP	good clinical practice
gMG	generalized myasthenia gravis
HBV	hepatitis B virus
HCV	hepatitis C virus
HEL-ABDEG™	full-length monoclonal antibody analog of ABDEG™
HIV	human immunodeficiency virus
IB	investigator's Brochure
ICF	informed consent form
ICH	International Council for Harmonisation
IEC	Independent Ethics Committee
IgG	immunoglobulin gamma
IMP	investigational medicinal product
IND	investigational new drug
IRB	Institutional Review Board
ITPV	intertreatment period visit in Part A
ITPEV	intertreatment period visit in Part B
IV	intravenous

IVIg	intravenous immunoglobulin
LRP4	lipoprotein receptor-related protein 4
MG	myasthenia gravis
MG-ADL	Myasthenia Gravis Activities of Daily Living
MGFA	Myasthenia Gravis Foundation of America
MuSK	muscle-specific kinase
NCI	National Cancer Institute
NSID	non-steroidal immunosuppressive drug
PD	pharmacodynamic(s)
PHQ-9	Patient Health Questionnaire item 9
PLEX	plasma exchange
PK	pharmacokinetic(s)
QMG	Quantitative Myasthenia Gravis
SAE	serious adverse event
SEB	study entry baseline
SoC	standard of care
SOP	standard operating procedures
SUSAR	suspected unexpected serious adverse reaction
TCB	treatment cycle baseline
TEAE	treatment-emergent adverse event
TPB	treatment period baseline
TPE	treatment period in Part B
TP _n B	subsequent treatment period baseline in Part A
TPE _n B	subsequent treatment period baseline in Part B

UNS	unscheduled visit
US	United States
WBC	white blood count
WHO(-DD)	World Health Organization (Drug Dictionary)

DEFINITION OF TERMS

Childbearing potential:	Women of childbearing potential are defined as all female participants unless they are postmenopausal (defined by continuous amenorrhea) for at least 2 years with a follicle-stimulating hormone (FSH) >40 IU/L or are surgically sterile (ie, who had a hysterectomy, bilateral oophorectomy, or have current documented tubal ligation or any other permanent female sterilization procedure).

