3.3. Tertiary Endpoints

Part A only:

- Total MG-ADL score changes compared to the treatment period baseline of the first cycle (TP₁B) and the corresponding TP_nB in AChR-Ab seropositive patients.
- Total MG-ADL score changes compared to TP₁B and the corresponding TP_nB in the overall population (AChR-Ab seropositive and AChR-Ab seronegative patients).
- Total QMG score changes compared to TP₁B and the corresponding TP_nB in AChR-Ab seropositive patients.
- Total QMG score changes compared to TP₁B and the corresponding TP_nB in the overall population (AChR-Ab seropositive and AChR-Ab seronegative patients).
- Percentage decrease (compared to TP₁B and the corresponding TP_nB) of total IgG level and IgG subtypes in efgartigimod (re-)treated patients.
- Percentage decrease (compared to TP₁B and the corresponding TP_nB) of autoantibodies (anti-AChR antibodies and anti-MuSK antibodies) in efgartigimod (re-)treated patients.

Part A and B:

- Incidence and prevalence of anti-drug antibodies (ADA) to efgartigimod.

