4. INVESTIGATIONAL PLAN

4.1. Summary of Trial Design

Methodology

DESCRIPTION

This is a 3-year (maximum), single-arm, open-label, multicenter, phase 3 follow-on trial of ARGX-113-1704 to evaluate the long-term safety and tolerability of efgartigimod in patients with gMG. The trial consists of 2 parts: Part A (1 year) and Part B (up to maximum 2 years or until efgartigimod becomes commercially available or another option to access efgartigimod is available, whichever option comes first. The additional part (Part B) was added to ARGX-113-1705 in order to provide the patients with the chance to have access to efgartigimod while it is not yet commercially available or available through another patient program. This extension will also enable additional long-term safety and tolerability data to be collected.

A variable number of treatment periods consisting of 4 weekly infusions of efgartigimod (10 mg/kg of body weight) infused over a period of 3 weeks will be administered to eligible patients on an “as needed basis” on top of their SoC. The time between treatment periods is based on the duration of the treatment effect and may vary from patient to patient and within each patient from period to period (patient-tailored approach).

The first visit of trial ARGX-113-1705 will coincide with the last visit of trial ARGX-113-1704 for each patient.

The SEB will be set at the first trial visit, while the baseline of each subsequent treatment period (TP_nB for Part A or TPE_nB for Part B) will be set at visit 1 of each corresponding treatment period.

ROLL-OVER

At the EoS visit of trial ARGX-113-1704, eligible patients will be offered the option to roll over into this trial. Patients in need of (re-)treatment in trial ARGX-113-1704 but who cannot complete a Treatment Cycle within the time frame of that trial, may immediately roll over to this trial to receive treatment with efgartigimod.

Patients who discontinued early from trial ARGX-113-1704 or discontinued early from randomized treatment for rescue or pregnancy reasons or for an SAE that is likely to result in a life-threatening situation or pose a serious safety risk in that trial will not be offered the option to roll over into this trial.

Patients who discontinued early from randomized treatment for other reasons and patients who had a temporary interruption from randomized treatment in trial ARGX-113-1704 may be offered the option to roll over into this trial.

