
SYNOPSIS Criteria for Evaluation:
 
3. TRIAL ENDPOINTS
 
3.1. Primary Endpoint
 
3.2. Secondary Endpoint
 
3.3. Tertiary Endpoints
	
Primary Endpoint:
 
 Incidence and severity of AEs, SAEs, vital signs, electrocardiogram (ECG) and laboratory assessments over 1 year in AChR-Ab seropositive patients. 
Secondary Endpoints:
 
 Incidence and severity of AEs, SAEs, vital signs, ECG and laboratory assessments over 1 year in the overall population (AChR-Ab seropositive patients and AChR-Ab seronegative patients). Incidence and severity of AEs, SAEs, vital signs, ECG and laboratory assessments at each Treatment Period in AChR-Ab seropositive patients. Incidence and severity of AEs, SAEs, vital signs, ECG and laboratory assessments at each Treatment Period in the overall population (AChR-Ab seropositive patients and AChR-Ab seronegative patients). 
Tertiary Endpoints
 
 To evaluate the disease severity as assessed by total MG-ADL score changes compared to SEB and the corresponding TP_nB in AChR-Ab seropositive patients. To evaluate the disease severity as assessed by total MG-ADL score changes compared to SEB and the corresponding TP_nB in the overall population (AChR-Ab seropositive and AChR-Ab seronegative patients). To evaluate the disease severity as assessed by total QMG score changes compared to SEB and the corresponding TP_nB in AChR-Ab seropositive patients. To evaluate the disease severity as assessed by total QMG score changes compared to SEB and the 	
Endpoints streamlined to reflect what will actually be summarized and labels added to clarify what will be analyzed in Part A and Part B of the trial.
 
Corrected to reflect that changes from the treatment period baseline of the first cycle will be summarized (instead of changes from SEB) as patients might start the study with an intertreatment period.
 
“To evaluate the disease severity as assessed by” should not be part of an endpoint definition.
 
For Part B only immunogenicity will be characterized as a tertiary endpoint. Furthermore, only safety and tolerability will be followed up and no PD markers will be summarized.

Section	Change	Rationale

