1.1 STUDY OBJECTIVES

According to the protocol, the primary objective of this study is:

- To evaluate the long-term safety and tolerability of ARGX-113 in acetylcholine receptor antibody (AChR-Ab) seropositive patients.

According to the protocol, the secondary objective of this study is:

- To evaluate the long-term safety and tolerability of ARGX-113 in the overall population (AChR-Ab seropositive and AChR-Ab seronegative patients).

According to the protocol, the tertiary objectives of part A of this study are:

- To evaluate the disease severity as assessed by total Myasthenia Gravis Activities of Daily Living (MG-ADL) score changes in AChR-Ab seropositive patients.
- To evaluate the disease severity as assessed by total MG-ADL score changes in the overall population (AChR-Ab seropositive patients and AChR-Ab seronegative patients).
- To evaluate disease severity as assessed by total Quantitative Myasthenia Gravis (QMG) score changes in AChR-Ab seropositive patients.
- To evaluate disease severity as assessed by total QMG score changes in the overall population (AChR-Ab seropositive patients and AChR-Ab seronegative patients).
- To evaluate the effect of ARGX-113 on pharmacodynamics (PD) (total immunoglobulin G [IgG], IgG subtypes, autoantibodies [anti-AChR antibodies and anti-muscle-specific kinase (MuSK) antibodies]).

According to the protocol, the tertiary objectives of part A and B of this study is:

- To evaluate the immunogenicity of ARGX-113.

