2.2 PHASES, PERIODS AND TIME POINTS

2.2.1 *Phases and periods*

All events and assessments will be allocated to phases and periods (see Table 1). A patient can start in 1705 in an inter-treatment period or in a cycle, depending on the patient status regarding the need for (re-)treatment upon roll-over. Each period following ITPO coincides with a cycle and includes the 4 administrations of efgartigimod and the inter-treatment period (ITP) visits. The length of the ITP is patient specific and can differ between the different periods. The number of patients may decline for each subsequent cycle.

	Statistical Analysis Plan	
ARGX-113-1705	Final Analysis	Final 1.0 of 20SEP2022

Table 1: phase/period definition

Phase	Period	Start	End
Treatment	ITP0	Earliest of (date of signing the informed consent form (ICF) and date of roll-over), with 00:00 added as time part.	First administration date/time in cycle 1 – 1 minute
	Cycle 1	First administration date/time in cycle 1	First administration date/time in next cycle – 1 minute or if last cycle: date of last contact, with 23:59 added as time part
	Cycle n	First administration date/time in cycle n	First administration date/time in next cycle – 1 minute or if last cycle: date of last contact, with 23:59 added as time part
	Cycle x	First administration date/time in cycle x	Date of last contact, with 23:59 added as time part

AEs and concomitant medications will be allocated to phases and periods as described in sections 5.1.2 and 3.5.2 respectively. All other assessments will be allocated to phases and periods based on the assessment date/time.

In case of (partially) missing date/time fields disabling allocation or date(time) equal to dosing date(time), information from visit label and protocol schedule of assessments (SoA) will be used to allocate to the correct period. If this is not possible, assessments will be allocated to the first possible cycle (not ITP0) unless the available parts of the assessments start or stop date/time provide evidence the assessments did not occur during that period.

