4. EFFICACY, PHARMACODYNAMICS AND ANTI-DRUG ANTIBODIES ANALYSES

4.1 EFFICACY

4.1.1 *Available data*

Efficacy will be assessed using MG-ADL (part A and B) and QMG (part A only).

4.1.2 *Endpoints and derivation rules*

1) Actual values and change from baseline and CnB in total MG-ADL score will be analysed descriptively and categorically.

Categories to be used for actual values in MG-ADL total score: 0, 1, 2, 3, 4, 5-7, 8-9, 10-12, 13-16, 17-20 and 21-24.

Categories to be used for changes from baseline and CnB in MG-ADL total score: >0, 0, -1, -2, -3, -4, -5, -6, -7, -8, -9, -10, <-10. Number of patients, percentages and cumulative percentages will be shown.

In addition to the planned timepoints, following timepoints will be shown for each cycle:

- Maximum drop from baseline and CnB in MG-ADL
- Minimum MG-ADL score: descriptively and categorically

Missing data will not be considered.

Analysis will be done on AChR-Ab seropositive patients, AChR-Ab seronegative patients and overall.

2) Actual values and change from baseline and CnB in total QMG score will be described descriptively and categorically as for the MG-ADL score. For the categorization of the QMG total score actual values a category of >24 will be added.

4.1.3 *Statistical analysis*

Summary statistics will be provided in terms of absolute values and changes from baseline (overall) and CnB (for each cycle) for MG-ADL and QMG total scores in AChR-Ab seropositive patients, AChR-Ab seronegative patients and the overall safety population.

Absolute values and changes from baseline (overall) and CnB (for each cycle) in MG-ADL and QMG total scores will also be categorized, including the number of patients within each category, the percentage, and the cumulative percentage.

See section 8 for a list of tables and listings.

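### The protocol defines MG-ADL change as a Part A only endpoint, but every MG-ADL table in the final SAP pools Parts A and B by cycle, and SAP 6.1 records no departure

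*SAP*

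**What the plan says.** Protocol 3.3 opens its tertiary endpoints with a Part A only group. That group includes "Total MG-ADL score changes compared to the treatment period baseline of the first cycle" (TP1B) and to the corresponding TPnB, in AChR-Ab seropositive patients and overall. Only anti-drug antibodies are listed for both parts. The synopsis and Protocol 2.3 agree. The baselines named are Part A baselines: Protocol 4.1 distinguishes "TP_nB for Part A or TPE_nB for Part B", and the List of Abbreviations gives TPnB as "subsequent treatment period baseline in Part A". The rationale for adding Part B in Appendix 7 agrees with the current text and is cited here for intent only: "For Part B only immunogenicity will be characterized as a tertiary endpoint".

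SAP 1.1 keeps that scope for the matching objectives: "According to the protocol, the tertiary objectives of part A of this study are", followed by the MG-ADL items. The analysis sections do not keep it. SAP 4.1.1 says "Efficacy will be assessed using MG-ADL (part A and B) and QMG (part A only"), and SAP 2.4.3 says "Part B data will not be tabulated separately but will be allocated to cycles like part A data". In SAP 2.2.1, Table 1, a cycle ends at the next cycle's first administration minus "1 minute or if last cycle: date of last contact, with 23:59 added as time part". SAP 6.1, the place for changes not covered by amendments, reads NAP.

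**The concern.** MG-ADL is the only Part A only endpoint that is also collected in Part B. QMG and the pharmacodynamic markers stop at EoA, so they limit themselves. MG-ADL needs an explicit limit and has none. Protocol 8 says that changes to the described analysis methods will be mentioned in the SAP.

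The parts are not interchangeable for this endpoint:

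- **Re-treatment.** In Part A it requires an MG-ADL total of at least 5 and a reduction of less than 2 points from the last baseline. In Part B it rests on the investigator's judgement. Cycle baselines are therefore reached under different rules.
- **Background therapy.** Changes are restricted in Part A (dose reductions between treatment periods are allowed) and unrestricted in Part B.
- **Visits between treatment periods.** They are every 30 days in Part A and every 90 days in Part B.

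A reader of the final tables would see cycle rows that can blend the two regimes and could not extract the endpoint the protocol promised.

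**Working it through.** **Table count (SAP 8.1).** Descriptive tables 14.2.1.1.1 to 14.2.1.1.5 give 5, and frequency tables 14.2.1.2.1 to 14.2.1.2.4 give 4, so 5 + 4 = 9. Tables 14.2.1.2.1 and 14.2.1.2.3 show actual values only, so 9 − 2 = 7 report change. Variants exist by AChR-Ab status, by region and excluding phone-call visits. None is by part.

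**Visit schedule against analysis windows.** Inputs: visit 4 on cycle day 22 ± 1; intertreatment visits every 30 ± 2 days (Part A) or 90 ± 7 days (Part B) after the previous visit (Protocol Tables 1 and 2). In SAP 2.2.4, Week 7 is days 36–63 and Week 7 + 4x runs from day 50 + 28x − 14 to day 50 + 28x + 13. This gives Week 11 = 64–91, Week 15 = 92–119 and Week 19 = 120–147.

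| Window | Part A cycle | Cycle started in Part B |
|---|---|---|
| Weeks 1, 2, 3 | days 8, 15, 22 | days 8, 15, 22 |
| Week 7 | 22 + 30 = 52 (49–55) | none |
| Week 11 | 22 + 60 = 82 (77–87) | none |
| Week 15 | 22 + 90 = 112 (105–119) | 22 + 90 = 112 (104–120; day 120 is Week 19) |
| Scheduled scores by about day 112 | 6 | 4 |

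The ranges add the visit windows: ±(1+2), ±(1+2+2) and ±(1+2+2+2) in Part A, and ±(1+7) in Part B. The counts assume that the patient has not been re-treated by then.

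In a cycle started in Part B, the Week 7 and Week 11 windows can be filled only by end-of-study, early-discontinuation, unscheduled or re-treatment visits. For example:

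- The earliest Part B re-treatment is 4 weeks to 31 days after visit 4: 22 + 28 = 50 to 22 + 31 = 53, in Week 7.
- An early-discontinuation visit 30 ± 2 days after a visit 4 dose falls on days 50–54, also in Week 7.
- The end-of-study date can be set by commercial availability.

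Such scores would share cells with routine Part A visits. The maximum drop and minimum score per cycle (SAP 4.1.2) also rest on fewer scheduled scores in Part B.

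**Cycles that cross EoA.** The last permitted Part A start is day 336 (Protocol 5.2.1), counting trial days from study entry. Visit 4 is then on day 336 + 21 = 357. EoA is on day 365 ± 7, that is 358–372. In cycle days this is 358 − 336 + 1 = 23 to 372 − 336 + 1 = 37, nominally 30. Every score in that cycle after cycle day 37 is a Part B score, yet Table 1 leaves it in a cycle begun in Part A. The same applies to any treated patient who enters Part B between treatment periods. Cycle number therefore does not identify the part.

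**The case against.** The strongest case against rests on six points.

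- **The pooling is disclosed.** SAP 2.4.3 and 4.1.1 state it plainly, and Protocol 8 does not name the section where a change must be mentioned. This stands as to transparency. But disclosing the pooling neither identifies it as a departure from Protocol 3.3 nor supplies the missing analysis.
- **By-cycle summaries and exploratory analyses are allowed** (Protocol 8.4.2 and 8), and MG-ADL is collected in Part B (Protocol 7.1). This supports adding pooled tables. It does not support replacing the defined analysis with them, and collection is not endpoint definition.
- **The conflict is narrower than 9 tables.** Protocol 8.4.2 needs only summary statistics, which 14.2.1.1.1 and 14.2.1.1.2 provide. It is fair that these two are the minimum needed to restore the protocol's analysis. The pooling still applies to all 9, and the frequency tables are the SAP's own way of presenting the same change.
- **Not every cycle row mixes the parts.** Protocol 7.2.2 plans its Part A blood volume on at most 6 treatment periods. This is a planning figure, not a cap: at nominal visits the shortest scheduled Part A cycle is 21 + 30 = 51 days, and starts at days 1, 52, 103, 154, 205, 256 and 307 give 7. Rows for high cycle numbers are nevertheless likely to be Part B only.
- **A Part A analysis may exist elsewhere.** SAP 1.5 refers to separate interim SAPs, which are not among the documents, and listing 16.2.6.1 gives scores by patient. A listing is not a summary, and an interim plan would not correct the final SAP.
- **No consequence for the results is shown.** Weeks 1–3 share one schedule, and pre-re-treatment scores also occur in Part A. This stands: neither size nor direction can be stated.

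**Conclusion.** The point holds. The final SAP extends a Part A only endpoint to both parts, tabulates it in no other way (0 of 9 tables, 0 of the 7 that report change), and does not record the departure. The difference in visit schedule affects tabulated results from about Week 7 of a cycle onward; the differences in re-treatment rule and background therapy can also affect earlier weeks. The rule in SAP 2.4.1 that only visits with at least 10 subjects are shown removes sparse visits but does not separate the parts in the rows that remain.

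The endpoint is tertiary and descriptive, so no error rate or sample size is involved, and the effect on mean change cannot be derived. The visit arithmetic assumes nominal schedules with the stated windows. The day-336 example assumes that trial day is counted from study entry. The change should be made, but it does not bear on the primary or secondary safety analyses.

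**What to change.** Add a part flag to the MG-ADL data. In SAP 2.4.3, 4.1 and 8.1, specify Part A versions of 14.2.1.1.1, 14.2.1.1.2, 14.2.1.2.2 and 14.2.1.2.4, covering AChR-Ab seropositive patients and the overall population. Include the maximum-drop and minimum-score rows, and use assessments up to and including EoA. State that cycles crossing EoA are truncated there, and that an EoA score which also serves as the first Part B baseline counts as the last Part A score. Keep the pooled tables as additional tables labelled Parts A and B. Record the Part B extension in SAP 6.1. Leave the safety tables as they are.

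The cost is one flag and four tables from data already collected. Later-cycle rows in the Part A tables will have smaller numbers, and some may fall below the 10-subject display rule.
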